	 Total anti-HER2 Immunoglobulin titers in sera by enzyme-linked immunosorbent assay (ELISA). Isotyping of anti-HER2 Immunoglobulins in sera (e.g. IgM, IgG (IgG1-4), IgD, IgE, IgA). Exploratory Endpoints: Percentage of patients with measurable disease at baseline achieving Complete Remission (CR) or Partial Response (PR) according to RECIST 1.1 as assessed by the investigator during routine follow up. Percentage of patients with Disease Control Rate (DCR) according to RECIST 1.1 as assessed by the investigator during routine follow up. Progression free survival (PFS) in patients with Stable Disease (SD), or PR, at the time of first dosing of ES2B-C001 alone or in combination with the adjuvant according to RECIST 1.1. Disease-free survival (DFS) in patients with CR at the time of first dosing of ES2B-C001 alone or in combination with the adjuvant according to RECIST 1.1. Overall survival (OS). This dose escalation part will be conducted according to an adapted 3+3
Study Period	 design. For each patient enrolled, there will be a: Screening period between 1 and 28 days prior to the first dose ES2B-C001. An out-patient treatment period of 12 weeks; Safety follow-up for ~6 weeks following the last dose of ES2B-C001. An end-of-study visit.
Study Design	The trial is a first-in-human, phase I, open-label, dose-escalating trial to assess the safety and tolerability of ES2B-C001 combined with [adjuvant] or without [adjuvant], in patients with human epidermal growth factor receptor 2 (HER2) expressing metastatic breast cancer.

Clinical Study: ES2B-C001-S01 EU CT No.: 2024-516333-12-00

Clinical Study: ES2B-C001-S01 EU CT No.: 2024-516333-12-00

The decision to escalate the dose to the next dosing cohort or initiate the expansion part will be taken by the sponsor based on the data safety monitoring board (DSMB) recommendations. The DSMB will base their recommendations on an evaluation of accumulated safety data and, if available, on immunogenicity data (antibody titers), whenever 3 patients of a specific cohort have received at least one dose, and the last patient completed the DLT observation period of 8 weeks.

Enrollment will be fully staggered in each of the populations, meaning that an observation period of 3 weeks plus 24 hours is foreseen before the second patient is dosed in one cohort. Dosing of the next subject in each cohort should ideally not take place until 1 week after the preceding patient has received the first dose.

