8.2.2.1 Initial Tumor Scans

At screening, patients require a baseline scan evaluated per RECIST 1.1. Tumor scans performed as part of routine clinical management are acceptable for screening if they are of acceptable diagnostic quality and performed within the allowed screening period, up to 28 days prior to start of ES2B-C001 administration.

Availability of CNS imaging in medical records, are required to evaluate radiographically detectable CNS metastases if applicable.

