8.2.2.2 Tumor Scans During the Trial

After enrollment, tumor scans should be performed at routine follow up every 12 weeks (± 2-week window) for MBC or more frequently if clinically indicated. If a patient discontinues trial treatment, tumor scans should be performed at the time of discontinuation (± 2-week window) unless previous scans were obtained within 2 weeks of discontinuation.

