8.3.5 Cardiac evaluations

8.3.5.1 Electrocardiograms

At screening a triplicate 12-lead ECG(s) will be obtained using an ECG machine that automatically calculates the heart rate and measures PR, QRS, QT, and QTc intervals. Holter ECG monitoring is acceptable to replace 12-lead ECG, provided the heart rate and measures PR, QRS, QT, and QTc intervals can be produced and entered in the eCRF.

During treatment, one 12-lead ECG(s) will be obtained at all dosing visits.

A triplicate 12-lead ECG is obtained at the End of Study visit at week 18 (+/- 14 days).

Triplicate ECGs include 3 individual ECG tracings obtained as closely as possible in succession, but no more than 2 minutes apart.

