9.2 Analysis Sets

Safety Set: will include all patients who received at least 1 dose of the trial drug. All safety/tolerability and DLT analyses will be performed using this analysis set and will be descriptive, with no statistical inference to be drawn from the data.

Immunogenicity Set: will include all patients who received at least 1 dose of the trial drug and have provided immunogenicity data. All immunogenicity analyses will be performed using this population.

Efficacy-evaluable Set: will include all patients receiving at least 1 dose of the trial drug and who have provided at least 1 tumor evaluation at baseline and 1 tumor evaluation following treatment administration.

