9.3.3 Exploratory endpoint analysis

Number and percentage of patients with Complete Remission (CR) or Partial Response (PR) (according to RECIST 1.1) at the latest assessment during the study period out of patients with measurable disease at baseline will be reported by study visit, dose level and patient population.

The number and percentage of patients with Disease Control Rate (DCR) according to RECIST 1.1 will be reported by dose level and patient population.

In addition, best percent change from baseline in sum of target tumor measurements will be summarized and presented graphically.

Progression free survival (PFS) in patients with SD, PR, or CR at the time of first dosing according to RECIST 1.1. will be evaluated using Kaplan-Meier estimate by dose level and patient population.

Overall survival (OS) will be evaluated using Kaplan-Meier estimate by dose level and patient population.

Exploratory endpoint analysis will be done on Efficacy-evaluable Set.

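### OS, PFS and response rates are restricted to patients with a post-treatment tumour evaluation, so early unscanned deaths disappear; section 9.3.3 also conflicts with Table 3 on PFS and DFS

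*Protocol*

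**What the plan says.** Section 9.3.3 lists the exploratory analyses: CR or PR, DCR, best percent change in target lesions, Kaplan-Meier PFS and Kaplan-Meier OS. It closes with one unqualified sentence: "Exploratory endpoint analysis will be done on Efficacy-evaluable Set". Section 9.2 restricts that set to dosed patients "who have provided at least 1 tumor evaluation at baseline and 1 tumor evaluation following treatment administration". Nothing exempts OS or PFS, and nothing says how a patient without a post-treatment evaluation is counted.

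On timing, section 8.2.2.2 states that "tumor scans should be performed at routine follow up every 12 weeks (± 2-week window) for MBC or more frequently if clinically indicated". It adds: "If a patient discontinues trial treatment, tumor scans should be performed at the time of discontinuation", with a two-week window. Under section 8.2.2.1 a routine baseline scan is accepted if "performed within the allowed screening period, up to 28 days prior to start of ES2B-C001 administration". Section 8.3.5.1 places the End of Study visit at week 18, plus or minus 14 days.

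On the time-to-event endpoints, the synopsis (section 1.1) defines "Progression free survival (PFS) in patients with Stable Disease (SD), or PR, at the time of first dosing" and a separate DFS endpoint for patients in CR at first dosing. Table 3 says the same, and section 8.2 lists DFS among the outcomes assessed. Section 9.3.3 instead analyses "Progression free survival (PFS) in patients with SD, PR, or CR at the time of first dosing" and does not mention DFS.

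**The concern.** Membership of the analysis set depends on something that happens after dosing. To be counted, a patient must live and stay on study until a tumour evaluation has been done. The endpoints are affected differently.

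- **OS:** every member has guaranteed survival from first dose to their first post-treatment evaluation. The curve cannot fall below 100% before the earliest such evaluation in the set. A death before evaluation is an OS event that the plan discards.
- **PFS:** the guarantee covers only deaths and progressions that occur without an evaluation. Progression seen at the first scan still counts.
- **DCR and ORR:** this is a selected denominator, not immortal time. Patients who die or leave unscanned cannot be in the numerator, so dropping them can raise the rate but never lower it. The rate stays the same only when the numerator is zero.

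Results are reported by dose level in cohorts of 3, possibly 6 or 9, so one patient matters. Section 4.2 names antitumour activity among the information a phase 1 trial should supply for designing phase 2.

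The PFS and DFS mismatch is a second fault. The protocol gives PFS two different populations and leaves a listed endpoint without an analysis.

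**Working it through.** The protocol gives no figure for the exploratory endpoints. Its patient numbers reproduce: 3 cohorts × 3 = 9 planned, and 3 × 9 = 27 at most (sections 4.1 and 9.1).

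**1. When the first routine scan falls.** Inputs: interval 12 ± 2 weeks (8.2.2.2), baseline scan 0 to 4 weeks before dose 1 (8.2.2.1), End of Study at week 18 (8.3.5.1).

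- Counted from the baseline scan: earliest −4 + 12 − 2 = week 6; latest 0 + 12 + 2 = week 14.
- As a share of follow-up: 6/18 = 33% to 14/18 = 78%.
- Counted from dosing, the window is week 10 to 14, or 56% to 78%.

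The protocol does not state the anchor, so week 6 is an inference. Clinically indicated or discontinuation scans can come earlier, so these are upper limits on the gap.

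**2. Share of deaths before that scan.** The protocol gives no mortality. Assume a constant hazard and 18-week mortality r of 5% to 20%. Then h = −ln(1 − r)/18, the probability of death before week t is p = 1 − exp(−ht), and the share of the 18-week deaths is p/r.

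| r | t (weeks) | p | p/r | True 18-week OS | 18-week OS given alive at t |
|---|---|---|---|---|---|
| 5% | 6 | 1.7% | 34% | 95% | 0.95/0.983 = 96.6% |
| 5% | 14 | 3.9% | 78% | 95% | 0.95/0.961 = 98.9% |
| 20% | 6 | 7.2% | 36% | 80% | 0.80/0.928 = 86.2% |
| 20% | 14 | 15.9% | 80% | 80% | 0.80/0.841 = 95.2% |

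The last column is what the plan would report if every death before t went unscanned, so it is the upper limit of the distortion.

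**3. Chance of dropping at least one patient.** This is 1 − (1 − m)^n, where m is the probability of being lost unscanned.

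| m (assumed) | n = 3 | n = 9 | n = 27 |
|---|---|---|---|
| 1.7% (deaths only, lowest row above) | 5% | 14% | 37% |
| 5% (deaths plus withdrawals) | 14% | 37% | 75% |
| 15% (deaths plus withdrawals) | 39% | 77% | 99% |

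**4. Examples that need no assumed rate.**

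- 1 of 9 dies unscanned before week 12 and the others survive: OS is 8/9 = 88.9% in all dosed patients and 8/8 = 100% in the Efficacy-evaluable Set.
- DCR with one patient unscanned: 2/3 = 66.7% becomes 2/2 = 100%; 4/6 = 66.7% becomes 4/5 = 80.0%; 6/9 = 66.7% becomes 6/8 = 75.0%.
- Pooled, with 14 of 27 controlled and 3 unscanned: 14/27 = 51.9% becomes 14/24 = 58.3%.

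**5. PFS and DFS side by side.**

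| Status at first dosing | Synopsis and Table 3 | Section 9.3.3 |
|---|---|---|
| SD or PR | PFS | PFS |
| CR | DFS | PFS; no DFS analysis |

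A smaller mismatch: section 9.3.3 scores response at the last assessment and also by visit, while Table 3 asks whether response was achieved. A responder who later progresses counts under Table 3 but not at the last assessment.

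**The case against.** The strongest reply is about importance. The trial tests no hypothesis, plans 9 patients and doses at most 27, and escalates on DLTs and safety. No decision rule uses OS, PFS or DCR, and section 4.2 speaks only in general terms. This stands and limits the severity, but it does not make a survival curve without its early deaths correct.

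The size is also uncertain. Eligibility criteria and the schedule table are not visible, so early mortality and loss cannot be judged. Discontinuation and clinically indicated scans would keep some patients in the set. A 5% floor for loss exceeds what the low end of the death model gives (1.7%). All of this is fair, and the figures should be read as ranges and upper limits. Those extra scans still cannot recover a patient who dies or withdraws before one is done.

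An evaluable-patient denominator for ORR and DCR is a disclosed convention, not an error in itself. That largely stands: the denominator point is weaker than the OS point. Section 9.2 also says evaluation rather than scan, and section 8.2.2 defines scan broadly; the exclusion works the same way.

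Deaths reported as SAEs would appear in the Safety Set tables. But section 8.4 does not count progression as an adverse event unless it leads to hospitalisation or death, so those tables cannot stand in for PFS or DCR.

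Finally, the SAP could settle details. Section 9, however, says the SAP elaborates the analyses described there, and it has already fixed both the set and the PFS population. Patients in CR are analysed, but under PFS.

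**Conclusion.** The concern holds. Followed as written, the plan removes deaths before the first post-treatment evaluation from OS and PFS and drops unscanned patients from the response denominators. This follows from the definitions alone. The section also contradicts the synopsis and Table 3 on the PFS population and leaves DFS without an analysis.

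The size depends on unstated rates. Under a constant hazard and 5% to 20% 18-week mortality, 34% to 80% of those deaths fall before the first routine scan. True 18-week survival of 80% could then be reported as up to 86% to 95%, and 95% as up to 97% to 99%. In a cohort of 3, a single unscanned patient can move DCR by 33 percentage points.

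The matter should be corrected but is not critical: the affected endpoints are exploratory and descriptive.

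**What to change.** In sections 9.2 and 9.3.3:

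- Analyse OS in all dosed patients; the Safety Set already defines them.
- Analyse PFS in all dosed patients with SD or PR at first dosing, and DFS in those with CR. Count death as an event and censor unscanned survivors. This follows the synopsis, Table 3 and section 8.2, which agree on the endpoints. If the sponsor prefers one combined PFS endpoint, those sections must change instead.
- Report DCR in all dosed patients with a baseline scan, and ORR in those with measurable disease. Count a missing post-baseline evaluation as not controlled or non-response.
- Keep the Efficacy-evaluable Set for best percent change and as a sensitivity analysis.
- Use one definition of response in section 9.3.3 and Table 3.

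The cost is wording, carried into the SAP. No new data, visits or patients are needed. Reported rates may be slightly less favourable.

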9.3.4 Safety analysis

Safety analysis will be evaluated on the Safety Set.

9.3.4.1 Adverse events

All recorded adverse events (AEs) will be summarized descriptively by preferred term and system organ class. Total number of AEs, total number of subjects with AE and percentage will be reported by dose level and patient population.

Additionally, AEs will be summarized by seriousness, severity (according to CTCAE v5.0), relationship to treatment and outcome.

9.3.4.2 Physical examination, Vital signs, ECOG, Cardiac evaluations, Clinical laboratory tests Safety variables will be analyzed descriptively according to general rules defined at the beginning of this section by study visit and patient population.

Clinical Study: ES2B-C001-S01 EU CT No.: 2024-516333-12-00

9.4 Protocol deviations

Protocol deviations will be listed per subject. Classification of protocol deviation will be specified in the respective plan.

10 General Considerations: Regulatory, Ethical and Trial Oversight

10.1 Regulatory and Ethical Considerations

- This trial will be conducted in accordance with the protocol and with the following:
 - Consensus ethical principles derived from international guidelines including the Declaration of Helsinki and Council for International Organizations of Medical Sciences (CIOMS) international ethical guidelines.
 - Applicable ICH Good Clinical Practice (GCP) guidelines
 - Applicable laws and regulations
- The protocol, protocol amendments, ICF, IB, and other relevant documents (e.g., advertisements) must be submitted to an IEC by the investigator and reviewed and approved by the IEC before the trial is initiated.
- Any amendments to the protocol will require IEC approval before implementation of changes made to the trial design, except for changes necessary to eliminate an immediate hazard to trial patients.
- Protocols and any substantial amendments to the protocol will require health authority approval prior to initiation except for changes necessary to eliminate an immediate hazard to trial patients.
- The investigator will be responsible for the following, as applicable:
 - Providing written summaries of the status of the trial to the IEC annually or more frequently in accordance with the requirements, policies, and procedures established by the IEC.
 - Notifying the IEC of SAEs or other significant safety findings as required by IEC procedures.
 - Providing oversight of the conduct of the trial at the site and adherence to requirements of 21 CFR, ICH guidelines, the IEC, European regulation 536/2014 for clinical studies, and all other applicable local regulations.

10.2 Financial Disclosure

The financing and insurance arrangements are documented in separate agreements.

10.3 Informed Consent Process

The principles of informed consent in the Declaration of Helsinki and GCP guidelines will be implemented before any protocol-specific procedures or interventions are carried out.

All subjects will be informed that participation is voluntary and that they can cease participation at any time without necessarily giving a reason and without any penalty or loss of benefits to which they are entitled.

Clinical Study: ES2B-C001-S01 EU CT No.: 2024-516333-12-00

- The investigator or the investigator's representative will explain the nature of the trial, including the risks and benefits, to the potential patient and answer all questions regarding the trial.
- The subject must give consent to participate prior to enrollment in the trial. This consent must be given in writing.
- The Investigator who conducts the informed consent discussion must also sign. The Investigator may delegate this responsibility to a suitably qualified member of the study team (e.g., Sub Investigator) if permitted by local regulations. This delegation of responsibility must be recorded in the Study File. By giving signed consent, the subject will confirm that his or her participation is voluntary and that he or she will follow the instructions of the Investigator and answer the questions asked. Signatures must be personally dated.
- The ICF must include all elements required by law, local regulations, GCP guidelines, and ICH guidelines, including consent to allow the Sponsor, Sponsor representative, or external regulatory auditor to review the subject's medical records. This gives permission to examine, analyze, verify, and reproduce any records and reports that are important to the evaluation of the trial.
- The medical record must include a statement that written informed consent was obtained before the patient was enrolled in the trial and the date the written consent was obtained.
- The signed and dated consent form will be kept by the Investigator. A copy of the ICF(s) must be provided to the patient.
- Patients must be reconsented to the most current version of the ICF(s) during their participation in the trial.

10.4 Recruitment strategy

 Patients will be recruited from the existing patient pool at the Department of Gynecology and the Department of Oncology, Medical University Vienna, Austria.

10.5 Data Protection and Data Retention

- Patients will be assigned a unique identifier by the sponsor. Any patient records or datasets
 that are transferred to the sponsor will contain the identifier only; patient names or any
 information which would make the patient identifiable will not be transferred.
- The patient must be informed that their personal trial-related data will be used by the sponsor in accordance with local data protection law. The level of disclosure must also be explained to the patient who will be required to give consent for their data to be used as described in the informed consent.
- The patient must be informed that their medical records may be examined by Clinical Quality Assurance auditors or other authorized personnel appointed by the sponsor, by appropriate IEC members, and by inspectors from regulatory authorities.
- The contract between sponsor and trial sites specifies responsibilities of the parties related data protection, including handling of data security breaches and respective communication and cooperation of the parties.

Clinical Study: ES2B-C001-S01 EU CT No.: 2024-516333-12-00

 Information technology systems used to collect, process, and store trial-related data are secured by technical and organizational security measures designed to protect such data against accidental or unlawful loss, alteration, or unauthorized disclosure or access. For eCRF, validated software Clinspire® will be used. The data will be stored on servers at Medical University of Vienna. The trained and designated study site staff as well as persons designated by the sponsor will have access to the data.

• The investigator shall retain all study records during the clinical investigation and for the period required by the applicable regulatory requirements or for at least 25 years after the premature termination or completion of the clinical investigation, whichever period is the longest. However, the investigator should contact the sponsor prior to destruction of any records or reports pertaining to the clinical investigation in order to ensure they no longer need to be retained. In addition, the sponsor should be contacted if the investigator plans to leave the site so that arrangements can be made for transfer of records.

10.6 Serious Deviation/Breach

If a deviation that is likely to affect to a significant degree the safety and rights of a subject or the reliability and robustness of the data generated in the clinical trial (serious deviation or breach) has occurred, the investigator should inform the sponsor and CRO within 24 hours.

10.7 Data safety monitoring board

The DSMB will constitute representatives from sponsor, CRO and the site (minimally represented by the treating principal investigator or designee). Additionally, up to 2 independent subject experts will be included. A dedicated charter will be established for the DSMB which will include responsibilities and instructions for the dose escalation procedure.

During the dose-escalation the DSMB will review accumulated safety data and available data on immunogenicity and make a recommendation to sponsor which dose may be used in the following dosing cohort.

Any safety concerns throughout the trial such as potential DLTs and/or events that may meet a criterion for initiation of rescue medication, will be escalated to the DSMB who will review accumulated safety data and may provide recommendations for trial adjustments, e.g. to:

- Recommend dose schedule optimizations to the treatment regimen during the trial.
- Recommend intermediate-level doses, provided the safety and immune response data indicate the need for intermediate doses.
- Evaluate if AEs reported as DLTs meet the DLT criteria.
- Recommend additional dose cohorts based on observed safety and tolerability data.
- Apply additional overnight stays for patients for safety precautions.
- Recommend additional patients to a cohort.
- Explore higher doses in the dose escalation part than recommended in the non-clinical toxicity package, if safety and immunogenicity data suggest a higher dose may be more optimal.

Clinical Study: ES2B-C001-S01 EU CT No.: 2024-516333-12-00

Written statements and conclusions of the DSMB decisions will be in place before implementing any adjustments to the trial.

11 Risk Management and Quality Assurance

